#### 4.11.2.1 Other Adverse Events of Interest

Selected MedDRA PTs will be combined to create grouped PTs or categories to further characterize risks associated with duvelisib. The following risks will be summarized as Adverse Event of Special Interest:

- Diarrhea/colitis
- Infections
  - All infections, excluding Pneumonia and COVID-19 infections
  - Pneumonia
  - COVID-19 infections
- Cutaneous reactions
- Non-infectious pneumonitis
- Neutropenia
- Hepatotoxicity (as defined by transaminase elevations)

The specific PTs that will be combined for each risk are defined in [Appendix 1](#).

For each risk, PTs will be summarized at the grouped PT and individual PT (and grouped SOC if applicable), at the subject level:

- TEAEs (all grades, all causalities)
- Treatment-related TEAEs (all grades)
- Grade 1 or 2 only TEAEs (all causalities)
- Grade 3 or higher TEAEs (all causalities)
- Treatment-emergent SAEs (all causalities)
- TEAEs resulting in dose holds
- TEAEs resulting in dose reductions
- TEAEs resulting in dose holds or reductions
- TEAEs resulting in discontinuation of study drug (all causalities)
- Time to initial onset (defined as AE start date – first dose date + 1)

In addition, the following summaries will be created for each grouped PT within each grouped SOC, at the event level:

- Summary of dose modifications
  - Number of events resulting in dose holds
  - Number of events resulting in dose reductions
  - Number of events resulting in dose holds or reductions
  - Number of events resulting in discontinuation of study drug
- Summary of outcome
  - Number of events resolved
  - Number of events resolved with sequelae
  - Number of events resolved or resolved with sequelae
  - Number of events not resolved
- Duration of AE

- Concomitant medications used to treat AEs (a specific list of concomitant medications associated with each risk will be provided)

For each subject and each AE, the worst severity recorded will be attributed and used in the by-severity summaries. Similarly, the worst causality (most related to treatment) will be attributed and used in the by-causality summaries. If causality is missing, the worst case will be assumed (related to treatment).

A by-subject listing of all AEs (including non-TEAEs) will be provided. This listing will be presented by treatment group and will include: center, subject identifier, age, sex, race, AE (SOC, PT, and verbatim term), date of onset, date of resolution, duration, severity, seriousness, action taken, outcome and causality.

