Clinical Chemistry, including Liver Function Tests	X	X	X	X		X	X		X	X		Liver function tests include LDH, serum ALT, serum AST, total and direct bilirubin, and ALP. Testing must be conducted, and results available, within 7 days prior to administration of first dose of duvelisib. Screening test results can be used for C1D1 if tests are performed within 7 days of C1D1.			
Immunoglobulin blood levels	X			X			X		X (even # cycles)			IgA, IgG, IgM			
Hematology	X	X	X	X	X	X	X		X	X		Hematology panel plus a 5-part differential. Testing must be conducted, and results available, within 7 days prior to administration of first dose of duvelisib. Screening test results can be used for C1D1 if tests are performed within 7 days of C1D1.			
Urinalysis	X	X		X			X		X	X		Qualitative analysis for protein performed at Screening, at C1D1, C2D1 and C6D1. If positive, quantitative analysis is needed if not previously noted as part of medical history. Testing must be conducted, and results available, within 7 days			

Activity	Screening D-30 to D-1	Cycle 1					Cycle 2		Cycle 3+	EoT ^a	Safety F/U ^b 30d (+7) postdose		Notes
		D1	D14 (-3)	D29 (+3)	D43 (±3)	D57 (±3)	D1 (±3)	D14 (-3)					
													prior to administration of first dose of duvelisib. Screening test results can be used for C1D1 if tests are performed within 7 days of C1D1.
ECOG Performance Status	X	X		X			X		X	X			If the ECOG Performance Status assessed at Screening is performed within 7 days of C1D1, the Screening assessment can be used and does not need to be repeated at C1D1 (predose).
EQ-5D-3L Questionnaire	X	X		X			X		X	X			Administered predose and prior to other procedures during treatment visits
Pharmacokinetic and Biomarker Assessments		X	X	X		X	X	X	X see note				For Cycles ≥ 3, obtain stool sample if subject has Grade ≥ 3 diarrhea or colitis. Request representative fragment of tissue and/or representative section of paraffin block from biopsy if taken for colitis or Grade ≥ 3 diarrhea.
	See Table 2 for detailed schedule												
Duvelisib Self-Administration Diary		X	X	X	X	X	X	X	X				First year on treatment only
Duvelisib Administration (Please see required and recommended prophylaxis in Section 6.6.1)		X (C1D14 AM dose in clinic)	X	X	X	X	X	X					Administration of the first dose should be scheduled to occur within 1 week after randomization. See Section 6.1 for dosing schedule.

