2.3. Benefit/Risk Assessment

2.3.1. Risk Assessment

As of 19 July 2018, in 588 subjects treated with duvelisib monotherapy in hematologic malignancy studies (see Section 6.3.4.1.2 in the IB), the most frequent treatment-emergent adverse events (TEAEs) ($\geq 20\%$ of subjects) reported were diarrhea/colitis (49.0%), neutropenia (34.7%), rash (34.7%), fatigue (33.2%), pyrexia (30.3%), cough (26.7%), nausea (26.0%), transaminase elevation (22.8%), musculoskeletal pain (22.6%), anemia (22.4%), upper respiratory tract infection (22.3%), and pneumonia (21.6%). The most frequently reported TEAEs, diarrhea and neutropenia, are amenable to early recognition and intervention. These events infrequently resulted in treatment discontinuation with management, including dose modifications and supportive care. Many of the more severe TEAEs, such as infections and hematologic abnormalities, are commonly observed in subjects with advanced B-cell malignancies. Adverse events (AEs) of special interest (AESIs), such as diarrhea, colitis, pneumonitis, rash, and transaminase elevations, have been well-described with the use of PI3K- δ inhibitors and immuno-oncology therapies. The most commonly occurring AEs infrequently resulted in treatment discontinuation, representing a manageable safety profile in subjects with advanced hematologic malignancies.

The identified risks for duvelisib treatment are infections, diarrhea/colitis, cutaneous reactions, pneumonitis, transaminase elevations, and neutropenia. Potential risks are hepatotoxicity and reproductive toxicity. Guidance on management of these AEs, including duvelisib dose interruptions and modifications, is provided in Section 6.6 and Section 6.7. Detailed information

about the known and expected risks and reasonably expected AEs of duvelisib may be found in the IB.

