#### 4.11.4 Clinical Laboratory Evaluation

Laboratory tests will be reported separately for hematology and blood chemistry.

For the purposes of presentation in both tables and listings, the following laboratory test results will be converted to the International System of Units (SI) before presentation: sodium, potassium, chloride, bicarbonate (or CO2), albumin, total protein, creatinine, uric acid, calcium, phosphorus, magnesium, glucose, total and direct bilirubin, alkaline phosphatase, red blood cell (RBC) count, hemoglobin, hematocrit, platelets, white blood cell count with 5-part differential

performed manually or by flow cytometry (lymphocytes, neutrophils, monocytes, basophils, and eosinophils), amylase, lipase, alanine aminotransferase (ALT), and aspartate aminotransferase (AST). Laboratory tests will be graded according to CTCAE Version 5.0 or higher.

If a laboratory test value is reported using a non-numeric qualifier (e.g., less than [<] a certain value or greater than [>] a certain value), the given numeric value will be used in the summary statistics, ignoring the non-numeric qualifier.

For laboratory tests graded by CTCAE, the following summary tables will be created by treatment arm:

- Summary of worst post-baseline value on treatment, regardless of baseline value according to the following categories:
  - Any grade
  - Grades 1 - 2
  - Grades 3 - 4
  - Grade 3
  - Grade 4
- Summary of worst post-baseline value on treatment that represents a worsening in grade from baseline according to the following categories:
  - Any grade
  - Grades 1 - 2
  - Grades 3 - 4
  - Grade 3
  - Grade 4

Laboratory tests with bi-directional grades (e.g., hyperglycemia and hypoglycemia) will be presented separately for each direction within each summary table.

For laboratory tests not graded by CTCAE, the following summary tables will be created by treatment arm:

- Summary of worst post-baseline value on treatment, regardless of baseline value according to the following categories:
  - Low (less than lower limit of normal)
  - Normal (greater than or equal to lower limit of normal and less than or equal to upper limit of normal)
  - High (greater than upper limit of normal)
- Summary of worst post-baseline value on treatment that represents a worsening from baseline according to the following categories:
  - Low (less than lower limit of normal)

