  - Normal (greater than or equal to lower limit of normal and less than or equal to upper limit of normal)
  - High (greater than upper limit of normal)

A subject will be defined as having a treatment-emergent laboratory abnormality if any of the following conditions are satisfied for a specific laboratory parameter:

- Laboratory result within the normal range at baseline and either a result below the lower limit of the normal range or above the upper limit of the normal range at any post-baseline time point on or before 30 days after the last dose of duvelisib.
- Laboratory result below the lower limit of the normal range at baseline and a laboratory result above the upper limit of the normal range at any post-baseline time point on or before 30 days after the last dose of duvelisib.
- Laboratory result above the upper limit of the normal range at baseline and a laboratory result below the lower limit of the normal range at any post-baseline time point on or before 30 days after the last dose of duvelisib.

A by-subject listing of all laboratory data will be provided by treatment group, with abnormal values flagged, and include center, subject identifier, age, sex, race, weight and visit. Laboratory reference ranges will also be listed.

Laboratory values (hematology, biochemistry and urinalysis) will be listed by subject and study time point including changes from baseline (with the exception of urinalysis). Baseline will be defined as described in [Section 4.2](#).

All values outside the clinical reference ranges will be flagged in the data listings. The abnormal values will be flagged with 'L' for values below the lower limit of the clinical reference range and 'H' for values above the upper limit of the clinical reference range and included in the listings. The Investigator will assess whether the values outside the clinical reference range are clinically significant and these will be reported as abnormal not clinically significant (NCS) or abnormal clinically significant (CS). Clinically significant laboratory values will be recorded by the Investigator as AEs.

Descriptive statistics (for non-categorical data including hematology and biochemistry) will be presented by cohort for both individual values (N, mean, SD, median, minimum, and maximum) and changes from baseline.

Boxplots over time (at each scheduled visit) will be provided for each laboratory parameter.

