**6 APPENDIX****Appendix 1: List of Preferred Terms for Adverse Events of Special Interest**

Grouped Term	Preferred Terms
All infections (excluding Pneumonia and COVID-19 infections)	All preferred terms under SOC = 'Infections Infections and infestations' excluding any preferred term containing the word 'pneumonia' and excluding any preferred terms included in the COVID-19 infections Grouped Term.
Diarrhea	Diarrhoea, Diarrhoea hemorrhagic, Defecation urgency
Colitis	Colitis, Colitis erosive, Enterocolitis, Enterocolitis hemorrhagic, Colitis microscopic, Necrotising colitis, Colitis ulcerative
Pneumonia	Pneumonia, any PT containing the word/string "pneumonia" except for "Pneumonia aspiration", Atypical pneumonia, Atypical mycobacterial pneumonia, Bronchopneumonia, Bronchopulmonary aspergillosis
Pneumonitis	Pneumonitis, Interstitial lung disease, lung infiltration, acute interstitial pneumonitis
Transaminase elevation	Alanine aminotransferase increased, Aspartate aminotransferase increased, Transaminases increased, Hypertransaminasaemia, Hepatic enzyme increased, Acute hepatic failure, Drug-induced liver injury, Hepatic failure, Hepatocellular injury, Hepatotoxicity
Cutaneous reactions	Dermatitis, Dermatitis allergic, Dermatitis bullous, Dermatitis exfoliative, Dermatitis psoriasiform, Drug eruption, Drug reaction with eosinophilia and systemic symptoms, Erythema, Erythema multiforme, Generalised erythema, Exfoliative rash, Rash, Rash generalised, Rash erythematous, Rash follicular, Rash macular, Rash maculo-papular, Rash maculovesicular, Rash papular, Rash papulosquamous, Rash pruritic, Rash pustular, Rash vesicular, Toxic skin eruption, Palmar erythema, Palmoplantar keratoderma, Palmar-plantar erythrodysesthesia syndrome, Perivascular dermatitis, Skin reaction, skin toxicity, Stevens-Johnson syndrome, Toxic epidermal necrolysis
Neutropenia	Neutropenia, Neutrophil count decreased
COVID-19 infections	Asymptomatic COVID-19, Congenital COVID-19, Coronavirus infection, Coronavirus test positive, COVID-19 pneumonia, COVID-19 treatment, Multisystem inflammatory syndrome in children, Post-acute COVID-19 syndrome, SARS-CoV-2 RNA decreased, SARS-CoV-2 RNA fluctuation, SARS-CoV-2 RNA increased, SARS-CoV-2 sepsis, SARS-CoV-2 test false negative, SARS-CoV-2 test positive, SARS-CoV-2 viraemia, Suspected COVID-19, Vaccine derived SARS-CoV-2 infection

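### No planned output counts subjects with concurrent ALT/AST and bilirubin elevation, and the hepatotoxicity AESI pools enzyme rises with liver-injury terms under a transaminase label

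*SAP*

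**What the plan says.** **Risk.** Protocol 2.3.1 includes transaminase elevations among the identified risks and then states: "Potential risks are hepatotoxicity and reproductive toxicity". The two are listed as different things.

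**Data.** The clinical chemistry row of the Schedule of Activities (Protocol 1.3, Table 1) specifies one panel: "Liver function tests include LDH, serum ALT, serum AST, total and direct bilirubin, and ALP".

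**Adverse events of special interest.** SAP 4.11.2.1 names the liver item "Hepatotoxicity (as defined by transaminase elevations". SAP Appendix 1 titles the corresponding group Transaminase elevation. It contains enzyme-increase terms and also "Acute hepatic failure, Drug-induced liver injury, Hepatic failure, Hepatocellular injury, Hepatotoxicity". It has no bilirubin or jaundice term.

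**Laboratory outputs.** In SAP 4.11.4 the main tables for CTCAE-graded tests are introduced as "Summary of worst post-baseline value on treatment, regardless of baseline value according to the following categories", followed by the same layout for worsening from baseline. A treatment-emergent abnormality is declared when the "conditions are satisfied for a specific laboratory parameter". For graphics, "Boxplots over time (at each scheduled visit) will be provided for each laboratory parameter". For individual data, "A by-subject listing of all laboratory data will be provided by treatment group, with abnormal values flagged".

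**The concern.** An isolated enzyme rise and an enzyme rise accompanied by raised bilirubin are different findings, and the second points more directly to the potential risk that the protocol lists separately. The SAP uses one label for both. A reader of the Hepatotoxicity row would see a total that may consist mostly of enzyme increases, with liver-injury terms added in and bilirubin absent.

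The laboratory tables do not fill the gap. They take the worst value of each test separately, so a subject's ALT peak and bilirubin peak are never linked, either within the subject or in time.

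The study's rationale is acceptable or improved safety with drug holidays, and it has no data monitoring committee (Protocol 9.6, SAP 4.11.6). The planned outputs therefore carry much of the safety description. At stake is whether the report can state, by arm, how many subjects had the combined pattern, including whether that number was zero.

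**Working it through.** The plan gives no figure for this point, so there is none to reproduce. The check reads each liver-related output in turn and asks whether the combined count could be obtained from it.

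**1. Outputs side by side**

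| Planned output | Source | Links ALT/AST and bilirubin in one subject? |
|---|---|---|
| AESI group, by grouped and individual preferred term | SAP 4.11.2.1, Appendix 1 | No; no bilirubin term, relies on reported terms |
| General TEAE tables by SOC and PT | SAP 4.11.2 | No; a bilirubin event appears on its own row |
| Worst post-baseline value, and worst worsening | SAP 4.11.4 | No; one test at a time |
| Treatment-emergent abnormality | SAP 4.11.4 | No; defined per parameter |
| Descriptive statistics and boxplots | SAP 4.11.4 | No; per parameter |
| By-subject laboratory listing | SAP 4.11.4 | Values are visible, but nothing is identified or counted |

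The SAP is not against joint summaries in general: 4.11.5.1 plans a combined systolic and diastolic blood pressure table.

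**2. Can the separate tables recover the joint count?**

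Let a be the number with raised ALT/AST, b the number with raised bilirubin and n the number treated. The number with both lies between max(0, a + b − n) and min(a, b).

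- n = 102 (approximate planned enrolment, Protocol 1.1).
- a = 0.228 × 102 = 23.3, taken as 23. The 22.8% is the TEAE rate for transaminase elevation among 588 monotherapy subjects (Protocol 2.3.1). Applying it to these schedules, and to laboratory values, is an assumption.
- b is not in the documents. Assumed rates of 2%, 5%, 10% and 20% give 2, 5, 10 and 20 subjects.

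| Assumed b | Lower bound | Upper bound |
|---|---|---|
| 2 | max(0, 23 + 2 − 102) = 0 | min(23, 2) = 2 |
| 5 | 0 | 5 |
| 10 | 0 | 10 |
| 20 | 0 | 20 |

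Within each row, the counts of subjects with each elevation are the same whether nobody or everybody with raised bilirubin also had raised transaminases. The upper bound equals b whenever b is no larger than a, so the result depends little on the 22.8%.

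**3. Would there be anything to count?** (illustration only)

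P(at least one in 102) = 1 − (1 − p)^102. The documents give no value for p.

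- p = 0.5%: 1 − 0.995^102 = 0.40
- p = 1%: 1 − 0.99^102 = 0.64
- p = 2%: 1 − 0.98^102 = 0.87

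A zero count is also worth reporting. The exact two-sided 95% upper limit with no cases is 1 − 0.025^(1/n): 3.6% for n = 102 and 7.0% for n = 51.

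**4. Baseline values that would confuse a joint count**

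Inclusion criterion 5 (Protocol 5.1) allows ALT and AST up to 3.0 × ULN, and bilirubin above 1.5 × ULN in Gilbert's syndrome. Some subjects could therefore meet, or nearly meet, a fixed multiple of ULN before the first dose. Any joint table has to show this.

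**The case against.** A reader might infer that hepatotoxicity is analysed solely as enzyme rises. The documents do not support that. Appendix 1 includes five liver-injury or liver-failure terms, and SAP 4.11.2.1 shows individual preferred terms, so each reported term has its own row with grade, seriousness, dose action and time to onset.

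A reader might also infer that a combined case would go unreported. That too is unsupported. The by-subject listing shows all values with abnormal ones flagged. SAP 4.11.4 has clinically significant laboratory values recorded as adverse events, so a bilirubin event would reach the general TEAE tables. Liver-related SAEs must be reported (Protocol 10.3, notes to Table 18).

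A third inference is that a joint table would show whether drug holidays change liver risk. It would not. Both arms use holidays, there is no continuous-dosing arm, and no formal comparison between arms is planned (Protocol 9.4.1).

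The other side can add that neither document defines hepatotoxicity as a combined elevation, that any numeric threshold is a reviewer's proposal, and that Protocol 9.4.4 and SAP 4.14 leave room for extra analyses.

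All of this stands, but the narrower gap remains. Adverse event terms depend on the investigator's judgement of clinical significance (Protocol 8.3.6), whereas a count derived from laboratory values does not. A listing shows the values but neither identifies nor totals the cases. The provision for extra analyses is optional and names no liver output.

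**Conclusion.** The point holds in limited form. The SAP's label merges a potential risk with an identified one. Its term group pools two kinds of event without a bilirubin or jaundice term. No planned table, figure or flag identifies or counts subjects with concurrent ALT/AST and bilirubin elevation, although the data come from one panel.

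This is a worthwhile, low-cost improvement to safety reporting. It has no bearing on the ORR analysis, sample size, type I error or power. The finding rests on reading the planned outputs, not on a rate. The 40% to 87% chance of at least one case is an illustration under an assumed true rate of 0.5% to 2%, and the joint-count ranges depend on assumed bilirubin rates. What the added output would give is a descriptive count per arm with a wide interval: no cases among 51 would still leave an upper limit of 7.0%.

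**What to change.** **In SAP 4.11.4**, add by treatment arm:

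- a descriptive table of subjects with ALT or AST elevation, and of those with concurrent total bilirubin elevation, with ALP shown;
- a scatter plot of peak ALT/AST against peak total bilirubin, in multiples of ULN. Peaks may fall at different visits, so the plot serves as a screen and the table applies the time window.

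Prespecify the reporting thresholds and the window that counts as concurrent. ALT/AST above 3 × ULN with total bilirubin above 2 × ULN is a proposal; the documents give no joint criterion. Flag subjects with raised baseline bilirubin (the Gilbert's exception) and those with raised baseline ALT/AST (entry allows up to 3.0 × ULN).

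**In SAP 4.11.2.1**, make the AESI label match the Appendix 1 title, Transaminase elevation, and report the liver-injury and liver-failure terms as a subtotal separate from the enzyme-increase terms. Appendix 1 already splits the diarrhea/colitis risk into two groups, so the layout has a precedent.

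**Cost.** One extra safety table, one figure and some SAP wording, all from data already collected. The thresholds serve reporting only; no dosing, holding or stopping rule changes.

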#### 4.11.3 Deaths, Serious Adverse Events, and Other Significant Adverse Events

A complete tabulation of all deaths occurring on study will be provided, which will include:

- All reported fatal AEs
  - Treatment-emergent fatal AEs by SOC and PT
    - Deaths within 30 days of duvelisib last dose by SOC and PT
    - Deaths > 30 days from duvelisib last dose by SOC and PT
  - Treatment-related treatment-emergent fatal AEs by SOC and PT
    - Deaths within 30 days of duvelisib last dose by SOC and PT
    - Deaths > 30 days from duvelisib last dose by SOC and PT
  - Fatal AEs reported that start > 30 days post duvelisib last dose by SOC and PT

The following listings will also be presented:

- A by-subject listing of all deaths that occurred during the study will be presented and will distinguish between deaths on treatment (through 30 days after last dose of duvelisib), fatal AEs outside the 30 day window, and deaths during survival follow-up
- A by-subject listing of all SAEs
- A by-subject listing of all AEs leading to discontinuation of study treatment
- A by-subject listing of all other significant AEs

Listings will follow the format described for AEs in [Section 4.11.2](#), if appropriate.

